10.3.4 Interim Analyses and Hierarchical Testing

The Statistical Analysis Plan will further describe the planned interim analyses.

Part A Combination Analyses Timing

One formal DFS interim combination analysis will be conducted at the time when approximately 88% (204) of the total DFS events in the combination and placebo arms have occurred and the time when the total enrollment of both Part A and Part B is expected to be complete. This formal comparison of DFS will allow for early stopping for superiority. The stopping boundaries at the interim and final analyses will be derived based on the exact number of DFS events using Lan-DeMets alpha spending function with O'Brien-Fleming boundaries. Note that if Part B enrollment is still ongoing at the time of observing the required number of events for the interim analysis and target number of events needed for the final analysis is projected to occur in a shorter time interval (approximately within 4 months), then the interim analysis of DFS will not be performed and only one final analysis of DFS will be conducted after the completion of enrollment in Part A and Part B (statistical significance of only one final analysis of DFS is 0.05 [two-sided]).

If the DFS combination analysis is significant, the OS combination analysis will be tested hierarchically. Formal OS interim combination analyses will be conducted at the time when the interim or final DFS combination analysis is significant. This formal comparison of OS will allow for early stopping for superiority.

The OS combination analyses occurring at the time when the DFS combination analysis is significant either after the Part A (approximately 800) participants randomized to the nivolumab + ipilimumab and placebo arms have a minimum of 20 or 26 months of follow-up, which are expected to occur at approximately 56 (62% of the total events) and 62 (70% of the total events) months from study initiation, respectively. These are at equivalent times when the DFS combination analyses of Part A are expected to occur. However, in the situation when the DFS combination analysis is significant at 56 months but OS is not significant at that time, the 62 month DFS analysis will not be necessary and so the second OS combination interim analysis will occur at 70 months (82% of the total events) rather than 62 months (70% of the total events). At the 56- and 62-month (or 70-month) OS combination analyses, approximately 178 and 201 (or 235) events are expected providing 41% and 53% (or 68%) power to detect overall interim OS HRs of 0.68 (P

< 0.009) and 0.70 ($P < 0.012$) (or 0.74, $P < 0.023$), respectively, at the pre-specified alpha level using the Lan DeMets alpha spending function.

The final OS combination analysis will take place after the Part A (approximately 800) participants randomized to the nivolumab + ipilimumab and placebo arms have a minimum of 48 months of follow-up, which is expected to occur approximately 84 months from the start of the study. At the time of the final OS combination analysis, approximately 287 events are expected ensuring 85% overall power to detect a final OS hazard ratio of 0.79 ($P < 0.045$).

Part B Monotherapy Analyses Timing

Similarly, 1 formal DFS interim monotherapy analysis will be conducted at the time when approximately 80% (122) of the total DFS events in the monotherapy and contemporaneous placebo arms have occurred. This formal comparison of DFS will allow for early stopping for superiority. The stopping boundaries at the interim and final analyses will be derived based on the exact number of DFS events using Lan-DeMets alpha spending function with O'Brien-Fleming boundaries. Note that if the target number of events for the interim analysis and final analysis are projected to occur in a shorter time interval (approximately within 6 months), then the interim analysis of DFS will not be performed and only one final analysis of DFS will be conducted (statistical significance of only one final analysis of DFS is 0.05 [two-sided]).

If the interim or final DFS monotherapy analysis is significant, the OS monotherapy analysis will be tested hierarchically. The final OS analysis will take place with approximately 182 events among all randomized Part B participants in nivolumab and placebo arms, which is expected to be at approximately 104 months from the start of the study, providing a minimum of 48 months of follow-up. Approximately 182 events are expected, ensuring 44% overall power to detect a HR of 0.73 ($P < 0.045$). Two formal OS interim monotherapy analyses will be conducted, which will allow for early stopping for superiority. The first and second interim analyses of OS are planned to occur with 102 events (56% of the targeted OS events) and 146 events (80% of the targeted OS events) among the randomized participants in nivolumab and placebo arms, which are expected to be at approximately 76 months and 90 months from the start of the study. Approximately 102 and 146 events are expected providing 8% and 27% power to detect overall interim OS HRs of 0.56 ($P < 0.006$) and 0.67 ($P < 0.023$), respectively, at the pre-specified alpha level using the Lan DeMets alpha spending function.

In addition to the formal planned interim analyses for DFS and OS, the DMC will have access to periodic unblinded interim reports of efficacy and safety to allow a risk/benefit assessment. Details will be included in the DMC charter.

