10.1.1 Part A: Combination Comparison of DFS

The combination comparison sample size is driven by the comparison of DFS between participants randomized to receive nivolumab + ipilimumab versus placebo. Approximately 800 participants will be randomized to the nivolumab + ipilimumab and placebo treatment arms in a 1:1 ratio with DFS medians of 111 and 72 months, respectively, rendering a 62-month study. Note the invocation of revprot03 will initiate the 1:1:2 (i.e. nivolumab + ipilimumab, placebo, nivolumab) randomization (see next section on Monotherapy Comparison of DFS).

Approximately 232 events among the approximately 800 contemporaneously randomized 1:1 participants are expected, ensuring 90% power to detect an average hazard ratio of 0.65 with an overall type I error of 0.05 (two-sided). The number of events and power were calculated assuming an exponential distribution and a delayed treatment effect of 3 months. This design yields a minimal HR of 0.764 ($P < 0.041$) when adjusting for interim analyses using Lan-DeMets alpha spending function.

Given accrual rates of 22 participants per month on average for the entire enrollment period, it is estimated that accrual of 800 participants (ie, 400 participants in each arm) will take approximately 36 months; it will take an additional approximately 26 months to observe the required number of events for the final DFS analysis.

There is 1 planned interim analysis of DFS. Stopping boundaries at the interim analyses will be derived based on the exact number of events using Lan-DeMets alpha spending function with O'Brien-Fleming boundaries. The DFS interim analysis is expected to occur at approximately 56 months when approximately 204 events are expected to have occurred. This will provide 83% power to detect an overall interim DFS HR of 0.743 ($P < 0.034$) at the pre-specified alpha level using the Lan-DeMets alpha spending function.

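### Section 10.3.4 attaches each OS power to the critical HR of that look, not to the design HR: with 287 deaths, power at a true HR of 0.79 is about 50%, not 85%

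*Combined protocol and SAP*

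**What the plan says.** Section 10.3.4 gives power for seven OS analyses, each with a number of deaths, an HR and a P threshold.

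- **Part A final** (287 deaths, P < 0.045): "approximately 287 events are expected ensuring 85% overall power to detect a final OS hazard ratio of 0.79".
- **Part A interims** (178 and 201, or 235, deaths): "providing 41% and 53% (or 68%) power to detect overall interim OS HRs of 0.68", followed by 0.70 and, for the alternative look, 0.74. The P thresholds are 0.009, 0.012 and 0.023.
- **Part B final** (182 deaths, P < 0.045): "ensuring 44% overall power to detect a HR of 0.73".
- **Part B interims** (102 and 146 deaths): "providing 8% and 27% power to detect overall interim OS HRs of 0.56" and 0.67. The P thresholds are 0.006 and 0.023.

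The supplied text gives no assumed OS HR and no OS medians. Section 10.3.4 says only that "The Statistical Analysis Plan will further describe the planned interim analyses".

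For the final DFS analysis, section 10.1.1 keeps the two quantities apart. The design effect is given as "ensuring 90% power to detect an average hazard ratio of 0.65 with an overall type I error of 0.05 (two-sided"), and the threshold separately: "This design yields a minimal HR of 0.764".

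**The concern.** An HR quoted with a power should be the true effect at which the design has that power. The HRs in section 10.3.4 do not behave like that. In Part B the strongest effect, 0.56, carries the lowest power (8%), and the quoted HR drifts towards 1 as deaths accumulate. That is how a significance threshold behaves.

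Taken literally, the section promises 85% power for a 21% reduction in the hazard of death in Part A. If the true figure is near 50%, a non-significant OS result could be over-read as evidence against a moderate survival benefit. In Part B the reader would be misled the other way at the quoted HRs. In neither part could the reader tell what survival effect was planned for.

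**Working it through.** **Inputs.** Deaths, P thresholds, HRs and powers are from section 10.3.4. Allocation is 1:1 in Part A (section 10.1.1) and 2:1 nivolumab to placebo in Part B (section 10.1.2). The log-rank test is two-sided (section 10.3.1).

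**Formulas.** With d deaths, k = 1/4 for 1:1 or 2/9 for 2:1, and z the normal quantile for the two-sided P:

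- critical HR = exp(−z / √(dk))
- single-look power at HR = Φ(|ln HR| √(dk) − z)
- cumulative power: multivariate normal, with correlation √(d_i/d_j) between looks.

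**Check on a correctly worded figure.** Final DFS, Part A: 232 events and P 0.041 give z = 2.044, √(232/4) = 7.616 and critical HR 0.765 (stated 0.764). Cumulative power at 0.65, with the 204-event interim, is 90.1% (stated 90%). The method reproduces the plan.

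**Final Part A OS.** z = 2.005 and √(287/4) = 8.471.

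- Critical HR = exp(−2.005/8.471) = 0.789, printed as 0.79.
- Power at 0.79 = Φ(0.2357 × 8.471 − 2.005) = Φ(−0.008) = 49.7%. For unrounded HRs from 0.785 to 0.795 it runs from 51.8% to 47.6%.
- Power at 0.70 = Φ(0.3567 × 8.471 − 2.005) = 84.5%.
- Deaths for 85% power at 0.79 = 4[(2.005 + 1.036)/ln 0.79]² ≈ 666.

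Other conventions do not recover 85% at 0.79: alpha 0.05 two-sided gives 51.5%, Freedman's formula 49.3%, and one-sided 0.05 63.8%.

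**All seven looks** (single-look power):

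| Part, deaths, P | Critical HR | HR printed | Power at printed HR | Power at 0.70 (A) or 0.75 (B) | Power stated |
|---|---|---|---|---|---|
| A, 178, 0.009 | 0.676 | 0.68 | 48.4% | 40.8% | 41% |
| A, 201, 0.012 | 0.702 | 0.70 | 50.6% | 50.6% | 53% |
| A, 235, 0.023 | 0.743 | 0.74 | 51.4% | 67.7% | 68% |
| A, 287, 0.045 | 0.789 | 0.79 | 49.7% | 84.5% | 85% |
| B, 102, 0.006 | 0.561 | 0.56 | 50.5% | 8.4% | 8% |
| B, 146, 0.023 | 0.671 | 0.67 | 50.3% | 26.3% | 27% |
| B, 182, 0.045 | 0.730 | 0.73 | 49.9% | 43.0% | 44% |

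Every printed HR equals the critical HR to two decimals.

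**Cumulative power, boundaries from Lan-DeMets O'Brien-Fleming spending.**

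- Part A at HR 0.70, looks at 178/201/287: 40.6%, 52.7%, 85.0% (stated 41%, 53%, 85%). With the second look at 235: 69.0% there (stated 68%) and 84.7% at the end.
- Part A at HR 0.79, final: 50.7% or 50.3%, depending on the second look.
- Part B at HR 0.75: 8.0%, 26.8%, 43.8% (stated 8%, 27%, 44%).
- Part B at each look's printed HR: about 49%, 51% and 51%.

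One HR per part therefore reproduces every stated power to within about one point. At 201 deaths the critical HR and the implied design HR coincide, so 53% at 0.70 is acceptable as worded.

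**Interim DFS.** Section 10.1.1 says "This will provide 83% power to detect an overall interim DFS HR of 0.743". With 204 events and P 0.034 the critical HR is 0.743. Power is 50.1% there and 83.1% at 0.65. In section 10.1.2, 122 events, P 0.025 and 2:1 allocation give critical HR 0.650. Power is 50.1% there and 40.8% at 0.68, against 40% stated for 0.65.

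**The case against.** The best defence is that this is a labelling matter in a secondary endpoint. OS is tested only if DFS succeeds, DFS drives the sample size, and the deaths, P thresholds and powers agree with one another. Each OS HR carries a nominal P, which hints at a threshold, and Tables 10.1.1-1 and 10.1.2-1 label the corresponding interim DFS values as critical HRs. A statistician would probably guess the intent. A separate SAP may also hold the OS design HRs.

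Much of this stands. The consequence is confined to reporting, the interim DFS sentences can be resolved from the tables, and the gap at 178 deaths is modest (41% against 48%). It does not make the final Part A statement true. Section 10.1.1 uses the same phrasing correctly for the final DFS design HR of 0.65, so one form of words carries two meanings. For OS there is no table and no design HR in the supplied text to settle which is meant.

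Two technical cautions also stand. First, using the printed P-values as boundaries for 178/235/287 or for the Part B looks spends slightly more than 0.05. Properly derived boundaries lower cumulative power by at most about one point, and the cumulative figures above use them. Second, the implied HRs assume proportional hazards. The DFS design assumes a 3-month delayed effect, and if OS did too, 0.70 and 0.75 are average HRs.

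**Conclusion.** The concern holds. Section 10.3.4 pairs OS powers with critical HRs. At a true HR of 0.79, final Part A OS has about 50% power (49.7% single look, 50 to 51% cumulative), against 85% stated. In Part B the stated 8%, 27% and 44% sit beside HRs at which power is about 50%. The stated powers are consistent with true HRs of about 0.70 (Part A) and 0.75 (Part B).

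The critical HRs need only the printed deaths, allocation and P thresholds. The cumulative figures also assume that the O'Brien-Fleming form, named only for DFS, applies to OS. The design HRs of 0.70 and 0.75 are back-solved and need the sponsor's confirmation. The underlying design calculation appears sound; what is wrong is the HR attached to each power, together with the absence of the OS design HR.

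**What to change.** - **Section 10.3.4:** state the OS design HR and survival assumptions for each part, including any delayed effect. The sponsor should confirm whether the HRs are 0.70 and 0.75. Attach every OS power to that HR, and label 0.68, 0.70, 0.74 and 0.79 (Part A) and 0.56, 0.67 and 0.73 (Part B) as critical HRs. A table in the style of Table 10.1.1-1 would do this.
- **Section 10.1.1:** give the interim DFS power as 83% at a true HR of 0.65, with critical HR 0.743.
- **Section 10.1.2:** give it as 40% at a true HR of 0.68, with critical HR 0.65.

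The cost is text only. Boundaries, event targets, sample size and timing do not change.

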Additionally, wording clarifications have been made for the interim overall survival (OS) analyses in Part B. If the first interim OS analysis were to reach the statistical significance with approximately 102 events, then the study would stop for early superiority for the formal OS comparison, and second interim OS analysis with approximately 127 events would not be performed. Due to this reason, the scenario with 127 OS events is redundant, and it is now omitted from the protocol to simplify the interim OS analyses plan in Part B. With this update, it is now clearly stated that the interim OS analyses in Part B are to be based on 102 and 146 events, as initially planned.

SUMMARY OF KEY CHANGES FOR PROTOCOL AMENDMENT 06		
Section Number & Title	Description of Change	Brief Rationale
Section 10.1.1 Part A: Combination Comparison of DFS	Typographical error has been updated within the section to align with values presented in Table 10.1.1-1 .	Typographical error has been corrected.
Section 10.1.2 : Part B: Monotherapy Comparison of DFS Table 10.1.2-2 : Part B Summary of Sample Size Parameters and Schedule of Monotherapy (without an Interim Analysis) Section 10.3.4 : Interim Analyses and Hierarchical Testing	Parameters and schedule of analysis for final DFS analysis alone in Part B were added. Also, summary Table 10.1.2-2 was added.	In the event that the target number of events needed for the final analysis is projected in a shorter time interval (approximately within 6 months), the interim analysis of DFS will not be performed and only one final analysis of DFS will be conducted in Part B.

SUMMARY OF KEY CHANGES FOR PROTOCOL AMENDMENT 06		
Section Number & Title	Description of Change	Brief Rationale
Section 10.3.4 : Interim Analyses and Hierarchical Testing	Language of the Part B OS interim analyses is clarified and one of the scenarios for the second interim OS analysis in Part B is omitted.	The Part B OS interim analyses language is updated to clearly state the plan for the pre-specified interim analyses. Also, OS interim analysis with approximately 127 events is a redundant scenario, and it is now omitted.
Section 10.3.1 : Efficacy Analyses	Stratum(s) with small number of participants.	In the event that there are fewer subjects randomized to a stratum, the participants in the stratum will be combined into another stratum.

TABLE OF CONTENTS

TITLE PAGE	1
DOCUMENT HISTORY	3
OVERALL RATIONALE FOR PROTOCOL AMENDMENT 06:	5

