In the event that the target number of events for the interim analysis and final analysis are projected in a shorter time interval (approximately within 6 months), then the interim analysis of DFS will not be performed and only one final analysis of DFS will be conducted after observing approximately 149 DFS events among the randomized participants in the nivolumab and placebo arms (required number of events since there is no alpha spending for DFS interim analysis). The 149 events are expected to provide 60% power to detect a DFS HR of 0.68 at alpha 0.05 (two-sided).

Table 10.1.2-1 summarizes sample size design parameters and schedule of primary endpoint analyses planned in this study.

Table 10.1.2-1: Part B Summary of Sample Size Parameters and Schedule of Monotherapy Analyses (with an Interim Analysis)

Primary Endpoint	DFS
Primary analysis population	All Randomized Participants in Nivolumab and Placebo Arms
Accrual rate per month	40 (or 30 2:1 to N and P)
Power	60%
Alpha	0.05 2-sided (0.025 at mono interim analysis and 0.043 at mono final analysis)
Hypothesized Median Control vs Experimental (Months)	72 vs 106
Hypothesized Hazard Ratio	0.68
Critical HR (HR at which a statistically significant difference would be observed) / Difference in median corresponding to a minimally significant effect size (Months)	0.71 / 29
Critical HR at mono interim analysis / Effect size (Months)	0.65 / 39
Expected events for mono interim analysis (percentage of target events)	122 (80%)
Timing of mono interim analysis from FPFV (Months)	76

Table 10.1.2-1: Part B Summary of Sample Size Parameters and Schedule of Monotherapy Analyses (with an Interim Analysis)

Primary Endpoint	DFS
Accrual Duration (Months)	20
Timing of final analysis (FA for mono) from FPFV (Months)	84
Sample size ^a	600
Target number of events (Event Goal)	153

^a East version 5.4 was used for sample size / power computation

Table 10.1.2-2 summarizes sample size design parameters and schedule of primary endpoint analysis with one final analysis alone.

Table 10.1.2-2: Part B Summary of Sample Size Parameters and Schedule of Monotherapy Analyses (without an Interim Analysis)

Primary Endpoint	DFS
Primary analysis population	All Randomized Participants in Nivolumab and Placebo Arms
Accrual rate per month	40 (or 30 2:1 to N and P)
Power	60%
Alpha	0.05 2-sided
Hypothesized Median Control vs Experimental (Months)	72 vs 106
Hypothesized Hazard Ratio	0.68

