Critical HR (HR at which a statistically significant difference would be observed) / Difference in median corresponding to a minimally significant effect size (Months)	0.71 / 29
Accrual Duration (Months)	20
Timing of final analysis (FA for mono) from FPFV (Months)	84
Sample size ^a	600
Target number of events (Event Goal)	149

^a East version 5.4 was used for sample size / power computation

10.1.3 Contribution of Components Analysis of DFS:

The contribution of components (CoC) will be assessed. The manner in which CoC will be measured is based on the hazard ratio and variance estimates computed for the contemporaneously randomized (approximately 200 vs 400) nivolumab + ipilimumab arm versus the nivolumab arm.

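### Part B's two fixed OS interims fit only a DFS win at the month-76 interim; after a later DFS win the 102-death look cannot be held, and the printed final OS level of 0.045 does not match the stated looks

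*Combined protocol and SAP*

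**What the plan says.** Section 10.3.4 (Part B Monotherapy Analyses Timing) sets the gate: "If the interim or final DFS monotherapy analysis is significant, the OS monotherapy analysis will be tested hierarchically". It also says "Two formal OS interim monotherapy analyses will be conducted, which will allow for early stopping for superiority", without regard to which DFS analysis succeeded. The schedule is: "The first and second interim analyses of OS are planned to occur with 102 events (56% of the targeted OS events) and 146 events" (80%), "which are expected to be at approximately 76 months and 90 months from the start of the study". The final OS analysis is at 182 deaths, about month 104. The printed levels are P<0.006 (HR 0.56, 8% power), P<0.023 (HR 0.67, 27%) and, at the final, P<0.045 (HR 0.73, 44% overall).

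Section 10.1.2 and Table 10.1.2-1 put the DFS interim at 122 events and month 76 (40% power) and the DFS final at 153 events and month 84 (60%). If the two are projected to fall within about 6 months of each other, "only one final analysis of DFS will be conducted after observing approximately 149 DFS events"; Table 10.1.2-2 places that analysis at month 84.

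The rationale for Amendment 06 explains why a further OS look was removed: "the scenario with 127 OS events is redundant, and it is now omitted from the protocol". The reason given is that a significant result at about 102 deaths would already have ended the formal OS comparison. In Part A, by contrast, Section 10.3.4 holds the OS look at whichever DFS analysis is significant and gives alternative months for the second look.

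**The concern.** The gate and the schedule agree on only one path. If DFS is first significant at month 84, the first OS look is dated 8 months before OS may be tested. The text does not say whether that look is dropped, moved to the DFS final or replaced, nor whether its alpha counts as spent. The reason for removing the 127-death look assumes that OS was tested at 102 deaths, which the gate rules out on these paths. Amendment 06 itself added the skipped-interim path, so this is a foreseen case. Left as it is, the timing and threshold of a confirmatory OS test would have to be settled after the DFS result is known.

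**Working it through.** **1. Branches, on the plan's own dates**

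| Branch | DFS analysis that opens OS | OS look at 102 deaths (month 76) | OS look tied to that DFS analysis | Later OS looks |
|---|---|---|---|---|
| DFS won at interim | month 76 | possible | yes | 146, 182 deaths |
| Interim missed, won at final | month 84 | before the gate | none | 146, 182 deaths |
| Interim skipped | month 84 (Table 10.1.2-2) | before the gate | none | 146, 182 deaths |

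Skipping requires a gap of about 6 months or less. If the interim count is reached at month 76, the only DFS analysis would come by about month 82, which is still after month 76.

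**2. How often this arises.** Inputs: 122/153 DFS events, HR 0.68, 2:1 allocation, two-sided 0.05, Lan-DeMets O'Brien-Fleming spending. Information is D × (1/3)(2/3) = 2D/9. This gives nominal levels 0.0241 and 0.0429, critical HRs 0.649 and 0.707, and power 40.3% and 60.4%, matching the plan's 0.025/0.043, 0.65/0.71 and 40%/60%. A first win at the final has probability 60.4% − 40.3% = 20.1%, and 20.1/60.4 is about one third of all DFS wins. If the interim is skipped, every DFS win comes at the only analysis.

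**3. Deaths when the gate opens.** Linear interpolation between 102 (month 76) and 146 (month 90):
- month 84: 102 + 44 × 8/14 = 127
- month 82: 102 + 44 × 6/14 = 121

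**4. OS levels.** Two-sided alpha spent at information fraction t = D/182 is 2 × 2[1 − Φ(2.2414/√t)]. Boundaries follow from the joint normal distribution with correlations √(Di/Dj), and critical HR = exp(−z/√(2D/9)). The plan states no OS design HR. Solving for its 44% overall power gives about 0.749.

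| Looks (deaths) | Nominal two-sided levels | Cumulative power |
|---|---|---|
| 102/146/182 | 0.0055/0.0229/0.0423 | 8.0%, 27.0%, 44.0% |
| 146/182 | 0.0247/0.0428 | 27.3%, 44.1% |
| 127/146/182 | 0.0146/0.0205/0.0420 | 18.1%, 26.7%, 43.9% |
| 127/182 | 0.0146/0.0456 | 18.1%, 44.4% |
| 102/127/182 | 0.0055/0.0129/0.0453 | 8.0%, 17.8%, 44.3% |

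The first row reproduces the plan's 0.006 and 0.023, its critical HRs (0.558 and 0.671 against 0.56 and 0.67) and its 8% and 27%. It does not reproduce the final 0.045. Of the three-look schedules, only 102/127/182 does. The printed final HR of 0.73 does not discriminate: 0.727 and 0.730 both round to it.

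**5. What the printed levels spend.** Overall two-sided alpha = 2 × [1 − P(all Z below their boundaries)].
- 102/146/182 at 0.006/0.023/0.045: 0.0524 (0.0522 with the unrounded interim levels)
- 146/182 at 0.023/0.045: 0.0510
- 146/182 at 0.023/0.0423: 0.0487

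**The case against.** The strongest reply is that the gate governs everything after it. If DFS is won at month 84, the 146-death look (month 90) and the 182-death final (month 104) still follow; only the 102-death look falls away, and overall power is 44.1% against 44.0%. That stands. It answers a stronger reading that a reader might infer, namely that the plan cannot be followed without breaking the hierarchy. Family-wise error would then be up to 1 − 0.95 × (1 − 0.0055) = 0.055, with independent tests and both nulls true. The documents do not support this: the figure requires testing OS before DFS has succeeded, which the gate forbids, and since death is itself a DFS event the two tests are not independent.

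Two more points stand in part. The OS looks are event-driven and the months approximate, so the clash depends on 102 deaths arriving before the DFS final or only analysis, as projected. And Section 10.3.4 defers further interim detail to the Statistical Analysis Plan; the material reviewed contains no separate SAP text, so rules by branch may exist there. Neither removes the conflict in the current protocol, which says both interims will be held and prints one set of levels.

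It is also fair that 127 deaths is nowhere expressly tied to the DFS final. That link comes from the interpolation above, and the explanation that 0.045 was carried over from a removed schedule is an inference from the matching figure.

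**Conclusion.** The point holds as an internal conflict in a confirmatory timing rule, plus one threshold that does not fit. In the branches where DFS is first won at its final or only analysis, the stated two-interim OS schedule cannot be carried out, and the plan does not say what replaces it. The missed look costs essentially no overall power. The threshold error is separate and applies even when no look is lost: 0.045 should be about 0.042 for 102/146/182, and using it takes overall two-sided alpha to about 0.052 (about 0.051 with only the later two looks). The excess is small.

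This rests on the plan's projected months, linear accrual of deaths between months 76 and 90, and O'Brien-Fleming-type spending for OS. Section 10.3.4 names Lan-DeMets for OS without the boundary type, but the two interim levels reproduce under that choice. The power figures also rest on the back-solved OS HR of about 0.75; the levels and alpha do not.

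**What to change.** In Section 10.3.4 (Part B) and the matching SAP text:

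- State that no formal OS test precedes DFS significance.
- As in Part A, hold the first OS look at the DFS analysis that first succeeds (about 102 deaths at the interim, about 121 to 127 at the final or only analysis). Alternatively, state that the 102-death look is dropped when DFS is not won at the interim.
- Derive Lan-DeMets O'Brien-Fleming levels from the looks actually held and the deaths observed, and print them by branch: for example 0.0055/0.0229/0.042 for 102/146/182, 0.0247/0.0428 for 146/182, and 0.0146/0.0205/0.042 for 127/146/182.
- Replace the final 0.045 to match the schedule kept.

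Two choices are the sponsor's, to be fixed before DFS is unblinded: whether to keep the 146-death look after one at about 127 deaths (some 6 months earlier), and whether the 102-death alpha counts as spent after a missed DFS interim. If it does, the level at 127 deaths is 0.0129 instead of 0.0146.

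The cost is one paragraph and a small table. No participants, visits or data collection change.
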